3.2 Study Population and Sites

The target population for this study consists of adult patients with SCH, BPI, or MDD, being treated with aripiprazole or for whom treatment with aripiprazole would be deemed appropriate by their treating physician, who have had at least one all-cause (including psychiatric) hospitalization or at least one psychiatric partial hospitalization within 60 days prior to study enrollment. Patient inclusion and exclusion criteria are outlined in sections 3.3.4 and 3.3.5 of the study protocol, respectively. Enrollment of a total of 640 patients is planned. To achieve balanced enrollment of the targeted diagnoses, a minimum enrollment of each diagnosis will be 25% or approximately 160 patients.

Participation of approximately 80 US physician sites [REDACTED] that provide care for a high volume of patients in the target population is anticipated.

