3.3.2 Physician Practice Eligibility

Enrollment of approximately 100 physician sites overall (ie, main study plus exploratory study) from the Anthem Network of providers in the United States (US) is planned for this study. HealthCore will identify potential physicians for the study by analyzing  to  to identify physicians who provide care for a high volume of patients who potentially meet basic inclusion criteria sufficient to support study enrollment goals.

Physicians (and patients) in the main study will be distinct from those in the exploratory study.

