3.5.1.6 Main Study: Interventional Phase (Day 1 to Day 180)

After the baseline visit, there are no mandated visits until Day 180. However, it is anticipated that patients will undergo medical evaluation at regular intervals. Data collected at these routine care visits, such as Abilify MyCite use changes and AEs (as described in [Section 4](#)), will be entered into the study database. Physicians are expected to regularly review the Abilify MyCite dashboard data during active Abilify MyCite use as consistent with routine care, approximately every 2 weeks.

At the time points indicated in [Table 3.5.1-1](#), the patient, caregiver (if applicable), and physician outcomes scales will be completed.

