7.3.1 Primary Endpoint

The primary endpoint compares the proportion of patients with all-cause hospitalizations between the Abilify MyCite and virtual matched control cohorts. The primary endpoint analysis will be a test of independent proportions. Standard methods for these analysis methods were developed by Fleiss and others¹⁵ and included in all statistical software systems.

These tests are directional in nature since the alternative hypothesis is that the proportions in the Abilify MyCite cohort will be lower than the proportions in the virtual controls.

Adjustments will be made to the alpha level to account for the one-tail nature of the alternative hypothesis (H_A).

- $H_0: P_1 - P_2 \geq 0$ versus $H_A: P_1 - P_2 < 0$

Where:

- P_1 = proportion of Abilify MyCite patients with all-cause hospitalization from study start date to Day 180

- P2 = proportion of virtual control patients with all-cause hospitalization from study start date to Day 180

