4.2 Sample Size Estimation

The primary endpoint for the study is the difference in the proportion of patients with at least 1 all-cause hospitalization for the Abilify MyCite versus virtual matched control cohorts from baseline to Day 180. The sample size calculation assumptions were based on input CCI [REDACTED] for patients diagnosed with SCH, BP1, or MDD who had at least 1 all-cause hospitalization or partial psychiatric hospitalization within the 60 days prior to enrollment. A control group event rate of 36.3% was estimated, weighted based on an expected study distribution of 25% patients with SCH, 25% with BP1, and 50% with MDD. Sample size calculations were based on testing 2 proportions using the Z-test with unpolled variance.

The study sample size of 447 patients was calculated based on the following assumptions, CCI [REDACTED]: 20% reduction in the proportion of patients with all-cause hospitalizations in the Abilify MyCite group versus the virtual matched control group (29.04% Abilify MyCite versus 36.30% virtual matched control), 1:3 (Abilify MyCite:virtual matched controls) matching, 80% power, and maintaining an overall alpha level of 0.05 with the level of significance in a superiority hypothesis of 0.025. Using a 30% dropout rate at 6 months, a sample size of 640 patients will need to be enrolled to ensure completion of 447 patients.

A virtual control group of approximately 1350 patients will be identified CCI [REDACTED] and matched to the final sample of Abilify MyCite patients. This will create 3 controls for every 1

Abilify MyCite patient, which reduces the required Abilify MyCite sample size as compared to a 1:1 match while maintaining statistical power. Controls will be matched to Abilify MyCite patients using a propensity score (please see section 3.4) [REDACTED]. If a sufficient population of controls is not identified to support matching in a 1:3 (Abilify MyCite:virtual matched controls) ratio, the matching ratio will be decreased sequentially to 1:2 followed by 1:1 if necessary.

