4.4 Primary Endpoint

The primary endpoint is the difference in the proportion of patients with at least 1 all-cause hospitalization for the Abilify MyCite versus virtual matched control cohorts from baseline to Day 180. The primary endpoint analysis will be a McNemar's paired sample chi-square test between the treatment cohorts.

This test is directional in nature as it is testing the alternative hypothesis (H_A) that the proportion patients hospitalized will be lower in the Abilify MyCite cohort than the virtual control cohort. Adjustments will be made to the alpha level to account for the one-tail nature of the alternative hypothesis.

- $H_0: P_1 - P_2 \geq 0$ versus $H_A: P_1 - P_2 < 0$

Where:

- P_1 = proportion of Abilify MyCite patients with all-cause hospitalization from baseline to Day 180
- P_2 = proportion of virtual control patients with all-cause hospitalization from baseline to Day 180

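### The primary test makes no allowance for clustering of MyCite patients in about 80 physician sites; if outcomes remain correlated within site after matching, its standard error is too small

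*SAP*

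**What the plan says.** SAP 3.2 plans for "Participation of approximately 80 US physician sites" in the main study. This fits protocol 3.3.2: "Enrollment of approximately 100 physician sites overall (ie, main study plus exploratory study").

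Controls are not recruited at those sites. SAP 3.4 defines a pool by plan enrollment, claims, age and diagnosis. It then matches within diagnosis, 1:3, on a propensity score. The finest readable geographic candidate variable is a four-level US region.

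The two documents name different primary tests. SAP 4.4: "The primary endpoint analysis will be a McNemar's paired sample chi-square test between the treatment cohorts". Protocol 7.3.1: "The primary endpoint analysis will be a test of independent proportions". Neither section contains a site term, a random effect or a robust variance. SAP 4.2 sizes the trial on "29.04% Abilify MyCite versus 36.30% virtual matched control" with "80% power, and maintaining an overall alpha level of 0.05 with the level of significance in a superiority hypothesis of 0.025", and uses no ICC or design effect. The only further adjustment mentioned is regression for covariates that remain imbalanced after matching (SAP 3.4).

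**The concern.** In a trial that randomizes within sites, a shared site effect falls on both arms and largely cancels. Here it falls on the MyCite arm, and nothing readable gives each MyCite patient controls from the same site. Any site-to-site variation left after matching therefore adds to the variance of the difference, and a test that treats patients or matched sets as independent does not count it.

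Two sources need to be kept apart. Background differences between practices, such as local admission habits or case mix that the propensity score misses, would inflate the false-positive rate. Differences in how physicians use the product (protocol 3.5.1.6: "Physicians are expected to regularly review the Abilify MyCite dashboard data during active Abilify MyCite use") would make the effect vary by site, which bears on power.

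At stake are the nominal one-sided 2.5% error rate and the stated 80% power. Both would be affected in the direction that favours the product or overstates the precision of the comparison.

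**Working it through.** **Inputs from the documents.** Rates p1 = 0.2904 and p2 = 0.3630; ratio 1:3; one-sided 0.025; 80% power; 447 completers; 30% dropout; 640 enrolled (all SAP 4.2); about 80 sites (SAP 3.2). On sidedness, SAP 4.4 says: "Adjustments will be made to the alpha level to account for the one-tail nature of the alternative hypothesis".

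**Assumptions.** The documents give neither an ICC nor the spread of site sizes. I use ICC 0.01 to 0.10, take equal site sizes first, and treat controls as independent.

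**The plan's own figure.**
- Pooled two-proportion formula: 441; with continuity correction: 459. Both are within 3% of 447.
- The unpooled form that the documents name: (1.960 + 0.842)² × (0.2061 + 0.2312/3) / 0.0726² = 422.
- Dropout: 447/0.70 = 639, in line with 640.

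**No clustering.** Var = 0.2061/447 + 0.2312/1341 = 0.000461 + 0.000172 = 0.000633, so SE = 0.02517. The MyCite arm supplies 0.000461/0.000633 = 72.8% of the variance. Power = Φ(0.0726/0.02517 − 1.960) = Φ(0.925) = 82.2%.

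**Design effect, MyCite arm only.** Completers per site: m = 447/80 = 5.59. DE = 1 + (m − 1) × ICC.
- Error under the null: at a common rate the SE grows by √((DE + 1/3)/(4/3)); actual error = P(Z > 1.960/growth).
- Power of a cluster-valid test: Var = 0.000461 × DE + 0.000172.

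Example, ICC 0.05: DE = 1 + 4.59 × 0.05 = 1.229. Growth = √(1.5627/1.3333) = 1.083, and P(Z > 1.810) = 3.5%. For power, SE = 0.02719 and Φ(2.670 − 1.960) = 76.1%.

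| ICC (assumed) | DE | True / planned SE | One-sided error, 1:3 independent test | Power at 447, cluster-valid test | Completers for 80% power, 80 sites (enrolled) |
|---|---|---|---|---|---|
| 0 | 1.00 | 1.000 | 2.5% | 82.2% | 422 (603) |
| 0.01 | 1.05 | 1.017 | 2.7% | 81.0% | 436 (623) |
| 0.02 | 1.09 | 1.033 | 2.9% | 79.8% | 451 (645) |
| 0.05 | 1.23 | 1.080 | 3.5% | 76.1% | 503 (719) |
| 0.10 | 1.46 | 1.155 | 4.6% | 70.5% | 635 (908) |

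**Where 80% power is lost.** It needs SE = 0.0726/2.802 = 0.02591, so DE = (0.0006716 − 0.0001724)/0.000461 = 1.083 and ICC = 0.083/4.59 = 0.018.

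**Simulation check (beta-binomial, 40,000 runs).** The 1:3 unpooled test gave 2.6%, 3.1%, 3.7% and 4.7% at ICC 0, 0.02, 0.05 and 0.10. A 1:1 McNemar test gave 2.5%, 2.6%, 3.1% and 3.8%.

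**Unequal site sizes.** With DE = 1 + ((1 + CV²)m − 1) × ICC and an assumed CV of 0.7, ICC 0.05 gives an error of 4.1% and power of 72.7%.

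**The case against.** Several counter-arguments are sound and limit the point.

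- **The size is assumed.** Nothing in the documents supports an ICC of 0.05 to 0.10 over one of 0.01, where nothing of practical importance happens. A reader might infer that the standard error is certainly too small; that follows only if a positive ICC remains after matching.
- **Some site variation may be removed.** Matching is within diagnosis, and the candidate variables include plan type, region, index month, antipsychotic fills, psychiatrist visits and comorbidities. Controls belong to the same insurer's plans as the study physicians' patients, and no readable criterion excludes patients of study physicians. Because text is redacted in SAP 3.4 and protocol 3.5.4, site-level matching cannot be fully ruled out. The test section, SAP 4.4, is readable and has no cluster term.
- **The dashboard mechanism does not inflate the error rate.** If the product has no effect, dashboard review creates no clustering of outcomes. Only background practice differences can raise the false-positive rate; the mechanism bears on power.
- **There is some reserve.** It is tempting to say that 80% power holds only at an ICC near zero. The named unpooled formula needs 422, not 447, so power starts at 82.2%.
- **The error figures in the table are not McNemar figures.** They describe the 1:3 independent comparison; the 1:1 McNemar test is inflated less.

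What remains is that neither named test protects against a residual site correlation, and the pairing in McNemar reduces the inflation without removing it.

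**Conclusion.** The concern holds in conditional form. For any positive residual ICC, both named tests understate the standard error, and the sample size ignores the loss. The loss is negligible at 0.01 and moderate at 0.05 to 0.10, where the true standard error is 8% to 15% larger than planned with equal site sizes, and more if sizes vary. These figures rest on the assumed ICC, about 80 sites, independent controls, and no site-level matching in the redacted text.

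A reader might also infer that a reported result is too optimistic. The documents do not support that: SAP 5.0 states that the study stopped after two subjects with no efficacy assessment, and SAP 5.2 marks efficacy analysis as not applicable. SAP 4.4 also specifies no confidence interval. The point concerns the soundness of the plan and any reuse of the design. It should be corrected, but it does not by itself invalidate the design.

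**What to change.** In SAP 4.4, and consistently in protocol 7.3.1, estimate the primary risk difference with a model for the matched sets, for example a weighted risk difference or GEE. Use a cluster-robust variance or a cluster bootstrap by MyCite site. Controls have no study site, so state that each matched set takes the site of its MyCite patient and is kept whole in resampling. Report the observed ICC. In SAP 4.2, state that 80% power assumes a residual ICC of no more than about 0.02 (0.018 by the calculation above).

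The cost is SAP wording and a standard procedure, slightly wider intervals, and a stated power that is conditional on the ICC. The robust variance corrects the error rate but does not restore power. If a larger ICC were thought likely, recruitment would have to rise, for example to 503 completers (719 enrolled) at 0.05.

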3.3 Randomization

Not applicable.

3.4 Virtual Matched Control Group

Enrolled patients will be matched to a virtual control group in a 1:3 ratio (enrolled patients on Abilify MyCite treatment : virtual matched controls). [REDACTED]

The matching process will be conducted after 6-month study data (or early termination data, if applicable) is collected for all Abilify MyCite patients. The virtual matched control group identified in this process will be used for all study analyses with a small amount of attrition expected for the 12-month analyses for controls who no longer have Anthem insurance coverage.

A pool of potential controls will first be identified using the following criteria:

- ≥ 1 day of enrollment in an Anthem-affiliated commercial, Medicaid, or Medicare health plan with medical and pharmacy benefits during the observation period (from date of First Patient In up until date of Last Patient In)¹³.
- ≥ 1 pharmacy claim for any atypical antipsychotic (excluding Abilify MyCite, clozapine, and long-acting injectable antipsychotics [LAIs]^{14,15}) during the observation period (Appendix F, Tables 2a and 2b).

¹³ Timeframe may be extended if additional samples are needed.

¹⁴ LAIs include: Aripiprazole monohydrate (Abilify Mantenna), Aripiprazole lauroxil (Aristada), Olanzapine pamoate (Zyprexa Relprevv), Paliperidone palmitate (Invega Sustenna), Paliperidone palmitate (Invega Tri state), Risperidone microspheres (Risperdal Consta)

¹⁵ Drugs include: Aripiprazole, Asenapine, Brexpiprazole, Cariprazine, Iloperidone, Paliperidone, Pimavanserin tartrate, Quetiapine fumarate, Risperidone, Ziprasidone, Ziprasidone Mesylate

- ≥ 1 all-cause hospitalization or partial psychiatric hospitalization¹⁶ that occurs at most 60 days prior to a pharmacy claim for any atypical antipsychotic (excluding Abilify MyCite, clozapine, and LAIs).
 - The earliest such pharmacy claim observed after the earliest observed hospitalization will be set as the initial (temporary) index date for each potential control.
 - For patients with ≥ 2 qualifying hospitalization/pharmacy claim episodes, an iterative process will be used to find the best match, and the final index date will be assigned accordingly.
- Age 18 to 63 on index date.
- ≥ 1 claim for SCH, BP1, or MDD on or before index date.
- No claims for pregnancy during the observation period.
- No claims for any LAI during the observation period.
- ≥ 180 days of medical and pharmacy enrollment prior to index date
- ≥ 180 days of medical and pharmacy enrollment following index date

Prior to matching, the pool of potential controls and the Abilify MyCite cohort will be stratified by psychiatric diagnosis (SCH, BP1, MDD). The Abilify MyCite cohort psychiatric diagnosis will be based on the psychiatric diagnosis recorded in the eCRF. The potential controls psychiatric diagnosis will be based on the psychiatric diagnosis identified [REDACTED] CCI. In the event that more than one of the qualifying psychiatric diagnoses is identified [REDACTED] CCI, the following hierarchy will be applied to potential controls: SCH>BP1>MDD.

From this pool of patients, combined with the active arm, logistic regression will be used within each psychiatric diagnosis to estimate a propensity score for each patient, where propensity refers to a patient's pre-index likelihood to be in the active arm. The dependent variable equals 1 for patients in the active arm and 0 for the controls. The following variables may be considered for inclusion in the propensity score model; a final determination will be made using descriptive study results on patient baseline characteristics.

- Age
- Gender
- Month of index date
- Plan type (commercial, Medicaid, or Medicare health plan with medical and pharmacy benefits)
- Number of fills for any atypical antipsychotic over 6-12 months prior to index date
- [REDACTED] CCI
- Occurrence/number of visits with a psychiatrist over 6-12 months prior to index date
- Comorbidities over 6-12 months prior to index date

¹⁶ Defined as a medical claim with place of service code = 52 ("Psychiatric Hospitalization"), or with HCPCS codes H0035 or S0201.

- Region of patient residence (Northeast, South, Midwest, West)

The estimated propensity scores will be used to match active arm patients to the virtual controls in a 1:3 ratio. Prior to assessing outcomes, the validity of the propensity score adjustment will be assessed by (1) graphically examining the overlap in propensity scores across treatment and control groups¹⁷, and (2) comparing balance in all baseline characteristics across the cohorts via standardized mean differences. A standardized mean difference >10% in absolute value will be used to indicate potential imbalance that may warrant further investigation or adjustment (e.g. through regression analysis).¹⁸ Propensity score models will be finalized prior to the assessment of outcomes.

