3.3.5 Patient Exclusion Criteria

For enrollment into the study, patients will be excluded if they fall under any of the following exclusion criteria.

Table 3.3.5-1 Exclusion Criteria	
1.	Any patient who participated in another clinical trial within 30 days of enrollment into the current study.
2.	Females who are breast-feeding and/or who are pregnant at the time of study enrollment, or who plan to become pregnant during the study.
3.	Patients who are currently being treated with a long-acting injectable antipsychotic.

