10.0 CCI

11.0 APPENDIX F: Coding tables

Table 1: Mental health ICD diagnosis codes

Condition	ICD-10 dx
Schizophrenia	F20.1x, F20.2x, F20.0x, F21.x, F20.5x, F20.89x, F20.3x, F20.9x
Depression	F32.x, F33.x
Bipolar disorder	F30.9x, F30.10x, F31.0x, F31.1x, F31.2x, F31.3x, F31.4x, F31.5x, F31.6x, F31.9x, F31.8x, F31.7x

Table 2a: Non-LAI atypical antipsychotic GPI Codes

Brand Name	Generic Name	GPI Code
FANAPT	Iloperidone	59070035000310 59070035000320 59070035000340 59070035000360 59070035000380 59070035000385 59070035000390
FANAPT TITRATION PACK	Iloperidone	59070035006320
INVEGA	Paliperidone	59070050007505 59070050007510 59070050007520 59070050007530
PALIPERIDONE ER	Paliperidone	59070050007505 59070050007510 59070050007520 59070050007530
RISPERDAL	Risperidone	59070070000303 59070070000306 59070070000310 59070070000320 59070070000330 59070070000340 59070070002010
RISPERDAL M-TAB	Risperidone	59070070007220 59070070007230 59070070007240 59070070007250 59070070007260
RISPERIDONE	Risperidone	59070070000303 59070070000306 59070070000310 59070070000320 59070070000330 59070070000340 59070070002010
RISPERIDONE M-TAB	Risperidone	59070070007220 59070070007230 59070070007240 59070070007250 59070070007260

RISPERIDONE ODT	Risperidone	59070070007210 59070070007220 59070070007230 59070070007240 59070070007250 59070070007260
QUETIAPINE FUMARATE	Quetiapine Fumarate	59153070100310 59153070100314 59153070100320 59153070100330 59153070100340 59153070100350
QUETIAPINE FUMARATE ER	Quetiapine Fumarate	59153070107505 59153070107515 59153070107520 59153070107530 59153070107540
SEROQUEL	Quetiapine Fumarate	59153070100310 59153070100314 59153070100320 59153070100330 59153070100340 59153070100350
SEROQUEL XR	Quetiapine Fumarate	59153070107505 59153070107515 59153070107520 59153070107530 59153070107540
SAPHRIS	Asenapine Maleate	59155015100710 59155015100720 59155015100730
OLANZAPINE	Olanzapine	59157060000305 59157060000310 59157060000315 59157060000320 59157060000330 59157060000340 59157060002120
OLANZAPINE ODT	Olanzapine	59157060007210 59157060007220 59157060007230 59157060007240

ZYPREXA	Olanzapine	59157060000305 59157060000310 59157060000315 59157060000320 59157060000330 59157060000340 59157060002120
ZYPREXA ZYDIS	Olanzapine	59157060007210 59157060007220 59157060007230 59157060007240
ABILIFY	Aripiprazole	59250015000305 59250015000310 59250015000320 59250015000330 59250015000340 59250015000350 59250015002020 59250015002050
ABILIFY DISCMELT	Aripiprazole	59250015007220 59250015007230

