ABILIFY MAINTENA	Aripiprazole	5925001500E430 5925001500E440 5925001500G230 5925001500G240
ARIPIPRAZOLE	Aripiprazole	59250015000305 59250015000310 59250015000320 59250015000330 59250015000340 59250015000350 59250015002020
ARIPIPRAZOLE ODT	Aripiprazole	59250015007220 59250015007230
REXULTI	Brexipiprazole	59250020000310 59250020000320 59250020000330 59250020000340 59250020000350 59250020000360
VRAYLAR	Cariprazine HCl	59400018100120 59400018100130

		59400018100140 59400018100150 5940001810B220
LATUDA	Lurasidone HCl	59400023100310 59400023100320 59400023100330 59400023100340 59400023100350
NUPLAZID	Pimavanserin Tartrate	59400028200320
GEODON	Ziprasidone HCl	59400085100120 59400085100130 59400085100140 59400085100150
ZIPRASIDONE HCL	Ziprasidone HCl	59400085100120 59400085100130 59400085100140 59400085100150
GEODON	Ziprasidone Mesylate	59400085202120

Table 2b: LAI atypical antipsychotic GPI Codes

Brand Name	Generic Name	GPI Code
INVEGA SUSTENNA	Paliperidone Palmitate	59070050101837 59070050101838 59070050101839 59070050101840 59070050101845
INVEGA TRINZA	Paliperidone Palmitate	59070050101850 59070050101860 59070050101870 59070050101880
RISPERDAL CONSTA	Risperidone Microspheres	59070070101910 59070070101920 59070070101930 59070070101940
ZYPREXA RELPREVV	Olanzapine Pamoate	59157060101950 59157060101960 59157060101970
ABILIFY MAINTENA	Aripiprazole	59250015001920 59250015001930
ARISTADA	Aripiprazole Lauroxil	5925001520E420 5925001520E430 5925001520E440 5925001520E450

This page is a manifestation of an electronically captured signature

SIGNATURE PAGE

Document Name: P31613217 Statistical Analysis PLaN

Document Number: 1000055470

Document Version: 3.0

Signed by	Meaning of Signature	Server Date (dd-MMM- yyyy hh:min) - UTC timezone
PPD	Biostatistics Approval	14-Oct-2019 21:18:24
PPD	Clinical Approval	14-Oct-2019 19:01:03

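### As coded, the control-group LAI screen covers only atypical injectables under drug-product codes, whereas the MyCite exclusion covers every long-acting injectable antipsychotic

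*SAP*

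**What the plan says.** For the MyCite arm, Protocol 3.3.5, item 3, excludes "Patients who are currently being treated with a long-acting injectable antipsychotic". It sets no limit by drug class, product or billing route.

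For controls, SAP 3.4 requires "No claims for any LAI during the observation period". Two other parts of the SAP give this rule its content:

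- Footnote 14 to SAP 3.4 reads "LAIs include: Aripiprazole monohydrate (Abilify Mantenna), Aripiprazole lauroxil (Aristada), Olanzapine pamoate (Zyprexa Relprevv" and continues with two paliperidone palmitate products and risperidone microspheres. That makes six products, all atypical.
- The only LAI code list is in Appendix F, headed "Table 2b: LAI atypical antipsychotic GPI Codes". It holds the same six products, under GPI codes.

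A control must also have "≥ 1 pharmacy claim for any atypical antipsychotic" other than MyCite, clozapine or an LAI, following a hospitalization by at most 60 days. Using an LAI alone therefore does not admit anyone.

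Elsewhere SAP 3.4 does give medical-claim codes where it needs them. Footnote 16 defines a partial psychiatric hospitalization by place of service "or with HCPCS codes H0035 or S0201". No such code is given for an LAI.

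**The concern.** The comparison is not randomized (SAP 3.3), so it rests on the two groups sharing eligibility rules and then being matched. Here the worded rules agree on class, but the list that would carry out the control rule is narrower than the MyCite exclusion. A patient on a first-generation depot is barred from one arm and can pass the coded screen for the other.

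Matching is not shown to repair this. Among the visible candidate covariates in SAP 3.4, the nearest is a count of atypical antipsychotic fills; none measures injectable use. One covariate is blacked out, and the list is only of variables that may be considered.

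If patients on unlisted injectables have a different 180-day hospitalization rate from other controls, the control rate moves, and the primary difference moves with it. A higher rate among them would flatter MyCite; a lower rate would count against it.

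**Working it through.** **Step 1: the rules side by side**

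| Feature | MyCite arm (Protocol 3.3.5) | Controls (SAP 3.4, Appendix F) |
|---|---|---|
| Class, as worded | any LAI | any LAI |
| Class, as listed or coded | no list; judged at the site | six atypical products |
| First-generation depots | barred | in neither footnote 14 nor Table 2b |
| Source of evidence | current treatment, known to the physician | claims, type not stated; GPI codes only |

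**Step 2: does the code table complete the footnote?** Footnote 15, on oral drugs, is also worded as *include* and omits olanzapine and lurasidone, yet Table 2a supplies codes for both. So an incomplete footnote can be made good by its table. Table 2b adds no drug beyond footnote 14, so a programmer following the SAP has no first-generation code to run.

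**Step 3: one patient through both screens.** Take a plan member with schizophrenia, discharged from hospital, on a first-generation depot, who fills an oral atypical within 60 days after the admission and meets the age, enrollment and pregnancy criteria. As a MyCite candidate, this patient is excluded by item 3. As a potential control, the oral fill sets an index date and no Table 2b code appears, so the patient stays in the pool.

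**Step 4: size.** The plan's figures (Protocol 7.1, SAP 4.2):

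- 36.30% × (1 − 0.20) = 29.04%, so the planned difference is 7.26 points.
- 447 / (1 − 0.30) = 638.6, against 640 stated.
- The 447 is approached by the pooled formula (441) or with a continuity correction (459). The unpooled formula that the text names gives 422. The present point does not depend on this.

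The documents give no share of controls on unlisted LAIs and no event rate for them, so what follows is assumed. Suppose the affected controls lie in the schizophrenia stratum, s = 25% of the expected distribution. Let f be the share of that stratum affected and d the difference in event rate.

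Shift in control rate = s × f × d

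| f | Share of all controls (s × f) | d (points) | Shift (points) | Shift / 7.26 |
|---|---|---|---|---|
| 2% | 0.5% | ±10 | ±0.05 | 0.7% |
| 2% | 0.5% | ±20 | ±0.10 | 1.4% |
| 10% | 2.5% | ±10 | ±0.25 | 3.4% |
| 10% | 2.5% | ±20 | ±0.50 | 6.9% |

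For the largest shift, take 447 versus 1341 patients (447 × 3), a one-sided 0.025 test and unpooled variance. The chance of a significant result is 82.2% at the planned rates, 76.7% with a control rate of 35.8%, and 86.9% with 36.8%. This treats the groups as independent and serves only to give scale.

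**The case against.** The best defence is that the rule itself is right. It speaks of any LAI, the abbreviation carries no class limit, and it refers to claims generally where neighbouring criteria specify pharmacy claims. Footnote 14 says *include*, so it need not be exhaustive. Footnote 14 and Tables 2a and 2b are cited at a different criterion, the atypical pharmacy claim, where an atypical-only list is natural; the LAI exclusion cites neither. Parts of Protocol 3.5.4 and SAP 3.4 are blacked out and might contain more.

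Much of this stands. A reader might infer that the SAP restricts the LAI check to pharmacy claims. It does not say so: for clinic-billed injections the defect is a missing code specification. A reader might also infer that patients on unlisted LAIs are simply admitted as controls. They are not: they need a qualifying oral fill after a hospitalization as well, which narrows the group.

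The defence does not remove the gap. Footnote 14 is attached to the abbreviation that the exclusion then uses, and Table 2b is the only visible LAI code list. Appendix F's coding tables are not redacted. A broadly worded rule with a narrow code list will be run as the narrow one unless someone intervenes.

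**Conclusion.** The coded LAI screen for controls is narrower than the MyCite exclusion. It can admit as controls some patients whom the protocol bars from the treated arm: certainly in code for first-generation depots, and possibly for LAIs billed as medical claims.

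The size cannot be derived from the documents. With 2–10% of schizophrenia controls affected and a rate 10–20 points different, the shift is about 0.05–0.5 points in either direction, or 1–7% of the planned difference. That rests on three assumptions: the share, the rate difference, and that the affected patients sit mainly in the schizophrenia stratum. Larger shares would give more.

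Two stronger readings are not supported:

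- One could apply 2–10% to all controls and reach 0.10 × 20 = 2.0 points, or 28% of 7.26. If the affected patients sit mainly in the schizophrenia quarter, that needs 10% / 25% = 40% of schizophrenia controls to be on an unlisted LAI plus an oral atypical after admission. Nothing in the documents suggests this.
- One could conclude that adherence in controls is understated. The visible text defines the secondary endpoint as days covered with antipsychotic medication and shows no algorithm. A depot patient with at least 80% coverage from fills would count as adherent, so any effect on PDC is open.

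This is a minor correction. SAP 5.0 records that the study ended after two patients with no efficacy assessment, so the flaw lies in the plan and affected no result.

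**What to change.** - In SAP 3.4, define an LAI as any long-acting injectable antipsychotic, first- or second-generation, and cite the code table at the control exclusion itself.
- Extend Table 2b with GPI codes for first-generation depots and medical-claim (HCPCS) codes for all LAIs, and retitle it to drop the atypical limit.
- State that the exclusion applies to both pharmacy and medical claims.
- Run the same list on MyCite patients' claims as a check on exclusion 3.

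Make the change together with the reconciliation of Tables 2a and 2b. The table headed "Table 2a: Non-LAI atypical antipsychotic GPI Codes" contains Abilify Maintena under "5925001500E430 5925001500E440 5925001500G230 5925001500G240", four codes that are absent from Table 2b. Correcting those alone would leave the present gap.

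The cost is SAP wording, a longer code list and minor programming. SAP 3.4 already requires 180 days of medical and pharmacy enrollment on each side of the index date, and Protocol 3.3.4 requires both benefits for MyCite patients, so no new data collection is needed. The control pool becomes slightly smaller.
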